13.3.3 Interim Analyses for Toxicity Post Surgery Immune-therapy

Under the same model described for futility and toxicity above, toxicities on immune-therapy after surgery will be monitored assuming an a priori probability of toxicity following Beta(0.4,1.6) in the current treatment against a constant rate of 0.20. For trial monitoring and decisions about future trials, extreme toxicities (TOXpost) will be defined as any grade 3 or higher adverse event that is possibly, probably, or definitely related to any therapy received on this protocol and occur after surgery between the first dose of adjuvant immune-therapy and the final dose received (up to 12 weeks) with the following exception. Any grade 3 adverse event that is potentially treatable with steroids will only count as an extreme toxicity if it does not improve to grade 2 or better within 2 weeks. Grade 3 nausea or vomiting that responds to anti-emetics within 72 hours and asymptomatic grade 3 or 4 lipase or amylase elevations will not count as TOXpost. The trial will be terminated if $\text{Prob}(\text{TOXpost} > 0.20 \mid \text{data}) > 0.9$. Following this rule, the trial will be terminated according to the following table once the first 3 patients are evaluable.

If there are this many patients (or more) with TOXpost	2	3	4	5	6	7	8
Stop the cohort if there are this many (or fewer) patients who are evaluable (have TOXpost or completed 4 weeks after first adjuvant immune-therapy dose without TOXpost)	3	6	9	13	17	21	25*

* Only patients who successfully have surgery and begin treatment with immune-therapy will be included. The table goes to 25 patients as the maximum of possible patients.

Three patients in each cohort will be accrued first. If 2 of the 3 patients have TOXpost, stop this portion of the trial and the adjuvant treatment will be declared as too toxic for this population. Check continuously as described above for toxicity. The operating characteristics (OCs) for this stopping rule for are summarized in the following table assuming all 25 or 15 patients in each cohort receive surgery and start adjuvant immune-therapy. Since we do not expect all 25 or 15 patients to enter this portion of the study, the OCs are slightly over-estimated.

		Stop if $\text{Prob}(\text{TOXpost} > 0.20 \mid \text{data}) > 0.90$					
		Cohort A (N=25)			Cohorts B and C (N=15)		

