True Toxicity Rate	Pr(stop early)	Mean Number of Patients	Median (25 th %ile, 75 th %ile)	Pr(stop early)	Mean Number of Patients	Median (25 th %ile, 75 th %ile)	
0.05	0.01	24.8	25 (25, 25)	0.01	14.9	15 (15, 15)	
0.10	0.04	24.2	25 (25, 25)	0.04	14.6	15 (15, 15)	
0.20	0.25	20.8	25 (24, 25)	0.20	13.1	15 (15, 15)	
0.30	0.62	15.2	16 (5, 25)	0.47	10.8	15 (5, 15)	
0.40	0.89	9.9	6 (3, 15)	0.73	8.3	6 (3, 15)	

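### Section 13.3.3 counts a patient as free of post-surgery toxicity at 4 weeks although the event window runs to 12, with no update rule and operating characteristics that ignore the delay

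*Combined protocol and SAP*

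**What the plan says.** Section 13.3.3 sets the post-surgery rule. Toxicity is "monitored assuming an a priori probability of toxicity following Beta(0.4,1.6) in the current treatment against a constant rate of 0.20", and the adjuvant part stops when the posterior probability of exceeding 0.20 is above 0.9. A TOXpost event is a qualifying related event of grade 3 or higher occurring "between the first dose of adjuvant immune-therapy and the final dose received (up to 12 weeks").

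The stopping table has two rows. The numerator row reads "If there are this many patients (or more) with TOXpost". The denominator row counts patients who have had TOXpost or have "completed 4 weeks after first adjuvant immune-therapy dose without TOXpost". The instruction is "Check continuously as described above for toxicity", starting when three patients are evaluable.

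The operating-characteristics table that follows is indexed by "True Toxicity Rate". Its one stated caveat is that fewer than 25 or 15 patients will reach adjuvant therapy. Tables 10.2 and 10.3 give adjuvant durvalumab at weeks 1, 5, 9 and 13. Section 13.4 requires previously reported patients to be brought up to date to week eight, but for futility information only.

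**The concern.** The 0.20 reference rate belongs to the whole window. At 4 weeks a patient has had one adjuvant durvalumab dose (cohort B also has oleclumab at weeks 1 and 3), and 8 of 12 weeks remain. Such a patient enters the denominator with the same weight as one who has finished the window. An interim check therefore compares a partly observed rate with a full-window limit, which lowers the posterior probability of excess toxicity at that check.

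At stake is how many further patients start an adjuvant combination before the rule reacts. The plan's readers also take the printed stopping probabilities as a description of the rule as it will be run.

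**Working it through.** **1. The printed rule.** With t events in n evaluable patients the posterior is Beta(0.4 + t, 1.6 + n − t). The rule stops if Pr(θ > 0.20) > 0.90. The largest n that stops for each t:

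| t | n | Pr at n | Pr at n + 1 |
|---|---|---|---|
| 2 | 3 | 0.907 | 0.846 |
| 3 | 6 | 0.914 | 0.873 |
| 4 | 9 | 0.925 | 0.895 |
| 5 | 13 | 0.913 | 0.886 |
| 6 | 17 | 0.907 | 0.883 |
| 7 | 21 | 0.904 | 0.882 |
| 8 | 25 | 0.903 | 0.883 |

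All seven printed boundaries reproduce.

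**2. The printed operating characteristics.** An exact binomial recursion was used, with a look after every patient from n = 3 and each outcome known when the patient is counted. Early stopping means a crossing at n < N.

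| True rate | N=25 computed (printed) | N=15 computed (printed) |
|---|---|---|
| 0.05 | 0.009 (0.01) | 0.009 (0.01) |
| 0.10 | 0.042 (0.04) | 0.040 (0.04) |
| 0.20 | 0.252 (0.25) | 0.201 (0.20) |
| 0.30 | 0.617 (0.62) | 0.467 (0.47) |
| 0.40 | 0.888 (0.89) | 0.732 (0.73) |

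All ten values match to rounding. The table therefore describes a rule with no delay between counting a patient and knowing the outcome.

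**3. What a 4-week count leaves unobserved.** The protocol gives no event timing, so take events as uniform over 12 weeks. At a true rate of 0.30, the 4-week rate is 0.30 × 4/12 = 0.10. A patient just counted as event-free still has probability (0.30 − 0.10)/(1 − 0.10) = 0.22 of TOXpost. At 0.40 the figures are 0.133 and (0.40 − 0.133)/(1 − 0.133) = 0.31. Both residual risks exceed 0.20.

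**4. Late events added as they occur.** Simulation with N=15, uniform timing and 0.5-2 adjuvant starts per month:

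| True rate | Printed | Stop at any time | Stop before last start, continuous checks | Stop before last start, checks only before each start |
|---|---|---|---|---|
| 0.40 | 0.73 | 0.70-0.75 | 0.59-0.72 | 0.54-0.69 |
| 0.30 | 0.47 | 0.42-0.47 | 0.38-0.44 | 0.33-0.42 |

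A separate simulation at 1-2 starts per month, checked only before each start, gave 0.57-0.65 and 0.30-0.38. The ranges are good to about three points.

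For N=25, with one third to one half of events in the first 4 weeks, crossing before the last evaluable patient is 0.56-0.61 at 0.30 (printed 0.62) and 0.86-0.88 at 0.40 (printed 0.89). The mean number started rises from 15.2 to 15.8-17.8 at 0.30, and from 9.9 to 10.5-13.3 at 0.40.

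**5. Status frozen at 4 weeks.** If a share f of events falls in the first 4 weeks, the rule sees the true rate × f. With f = 1/2, a true rate of 0.40 is seen as 0.40 × 1/2 = 0.20, and the plan's own 0.20 row applies: 0.20 for N=15 and 0.25 for N=25, against 0.73 and 0.89. With f = 1/3, a true rate of 0.30 is seen as 0.10, and stopping is 0.04 for both sizes.

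**6. Earlier events.** If all events fall within 4 weeks, stopping at 0.30 is 0.48-0.54 for N=15 and 0.64-0.67 for N=25, at or slightly above the printed values. Events then count at once while event-free patients wait 4 weeks.

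**The case against.** The strongest reply is that nothing in Section 13.3.3 closes a patient's record at 4 weeks. The numerator counts every patient with TOXpost, the event definition reaches 12 weeks and checking is continuous, so a week-6 event enters when it happens. This reply stands. A reader might infer from the table heading that the rule cannot reach its printed stopping probabilities. The documents do not support that: with late events added, stopping at any time is close to the printed figures.

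The size of the remaining loss also rests on inputs the protocol lacks. The 1-2 patients per month in Section 13.3 is an enrollment rate. Adjuvant starts will be fewer, because not all patients reach surgery, Section 5.1 lets patients choose chemotherapy instead, and cohorts B and C alternate in blocks of about five. Slower starts shrink the loss. The look schedule matters too: Section 13.3 ties checks to consent, which precedes the adjuvant start by the interval to surgery (3-10 weeks) plus 4-12 weeks. Neither simulated schedule is exactly that.

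Two further inferences should be avoided. That the 4-week criterion was carried over by mistake from the neoadjuvant table in Section 13.3.2 is conjecture. And saying that three of four durvalumab doses are still unobserved overstates the gap, because the week-13 dose falls at the end of the 12-week window. It is mainly the week-5 and week-9 doses whose events are missed.

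What the reply does not answer is the missing update instruction, given that Section 13.4 writes one for futility, and the operating characteristics that assume no delay.

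**Conclusion.** The mismatch is real and worth correcting. The evaluability point and the event window disagree, no text says how to carry a patient from week 4 to week 12, and the printed operating characteristics describe a rule without delay.

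Under the reading the text best supports, the effect is later stopping rather than a disabled rule. For cohorts B and C the loss in stopping before the last start is between about 1 point (0.73 − 0.72) and 19 points (0.73 − 0.54) at a true rate of 0.40, and between 3 (0.47 − 0.44) and 14 points (0.47 − 0.33) at 0.30. These sizes rest on uniform timing, 0.5-2 starts per month and all 15 patients starting adjuvant therapy. They shrink with slower starts or earlier events.

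The much larger loss under frozen status is not what the plan says, but the plan does not exclude it. A safety rule should not depend on which reading staff adopt.

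**What to change.** 1. Add to Section 13.3.3 that, at every check, TOXpost status is updated for every patient who has begun adjuvant immunotherapy, through the end of that patient's window (final dose received, up to 12 weeks).
2. Replace the 4-week criterion in the table heading. A patient with TOXpost, or whose window has closed without it, counts as 1. An event-free patient still in the window counts as weeks completed/12. The posterior formula accepts a fractional n. Example: 3 events, two patients past 12 weeks event-free and two event-free at 4 weeks. The present heading gives n = 7 and a posterior of 0.873, so the cohort continues. Weighting gives n = 3 + 2 + 2 × 4/12 = 5.67, below the boundary of 6, so it stops. State that the minimum of three applies to this weighted count.
3. Rerun the operating characteristics with delayed outcomes, stating the assumed start rate, event timing and look schedule.

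Simply requiring 12 weeks for event-free patients while counting events at once is not recommended without recalibrated boundaries. For N=15 it raises stopping at the 0.20 reference rate to about 0.25-0.37 (printed 0.20), whereas weighting keeps it at about 0.17-0.18.

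The cost is a heading, a few sentences and a rerun, with slightly less favourable printed stopping probabilities. The weights assume roughly even event timing, so the rerun should include an early-event case.

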13.4 Analysis Plan

Primary endpoint: Each combination regimen will be considered feasible if at least 80% of patients successfully undergo surgery. It will be infeasible if fewer than 60% of patients can undergo surgery. If the successful surgery rate is between 60% and 80%, then consideration will be given to toxicity, clinical outcome measures, and immune changes to determine whether this regimen warrants further investigation. The 95% posterior credible interval will be calculated for proportion of patients undergoing surgery. Adverse events will be tabulated.

Additional analyses: Demographic and patient baseline disease characteristics will be summarized for all patients. Descriptive tables and figures will be presented for immune markers. Overall (OS) and relapse-free survival (RFS) will be calculated and plotted by Kaplan-Meier methods[69]. Relationships between baseline characteristics, immune markers, and outcomes (response, OS, or RFS) will be explored with logistic or Cox[70] models as patient numbers allow. No formal hypotheses will be tested, but results will be used to design the next formal trial if toxicity and feasibility are reasonable for further investigation.

The Investigator is responsible for completing a futility/toxicity summary report, and submitting it to the IND Office Medical Affairs and Safety Group, for review and approval. This should be submitted after the first 3 evaluable patients per cohort, have surgery or 4 weeks after the first dose of immune-therapy, whichever comes first, and

every 2 to 4 evaluable patients thereafter, according to the schedule described in the toxicity/futility monitoring tables.

On every summary submission, futility information about previous reported patients will need to be updated to week eight.

A copy of the cohort summary should be placed in the Investigator's Regulatory Binder under "sponsor correspondence".

REFERENCES

1. Siegel, R., et al., *Cancer statistics, 2014*. CA Cancer J Clin, 2014. **64**(1): p. 9-29.
2. Scheele, J., et al., *Resection of colorectal liver metastases*. World J Surg, 1995. **19**(1): p. 59-71.
3. Adam, R. and E. Vinet, *Regional treatment of metastasis: surgery of colorectal liver metastases*. Ann Oncol, 2004. **15 Suppl 4**: p. iv103-6.
4. Parkin, D.M., et al., *Global cancer statistics, 2002*. CA Cancer J Clin, 2005. **55**(2): p. 74-108.

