1. OBJECTIVES

1.1. Primary Objective

Assess the safety and feasibility of adding Immune-therapy with durvalumab (MEDI4736) (anti-PD-L1) combined with either Tremelimumab (anti-CTLA-4) or Monalizumab (anti-NKG2A) or Oleclumab (MEDI9447) administered once pre-operatively and post-operatively in patients who are candidates for resection for colorectal cancer with liver or lung metastases (CRCLM).

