5. TREATMENT PLAN

5.1 Study Design and Duration

This study is an open-label, single center trial assessing the safety and feasibility of using perioperative neoadjuvant and adjuvant immune-therapy for resectable liver or lung metastases.

Cohort A will consist of neoadjuvant tremelimumab 75 mg IV flat dose and durvalumab 1500 mg IV flat dose. Adjuvant therapy will consist of 4 monthly doses of durvalumab 1500mg IV.

Cohort B will consist of neoadjuvant oleclumab 3000 mg IV flat dose followed by durvalumab 1500 mg IV flat dose. Adjuvant therapy will consist of 4 months of oleclumab every two weeks at 3000 mg IV flat dose and durvalumab every 4 weeks at 1500 mg IV flat dose. On days oleclumab and durvalumab are both administered, oleclumab will be given first (see Section 8.1.4).

Cohort C will consist of neoadjuvant durvalumab 1500 mg IV flat dose then Monalizumab 750mg IV flat dose. Adjuvant therapy will consist of 4 months of durvalumab 1500 mg IV flat dose and monolizumab 750 mg, both administered every four weeks.

[figure not shown]
Cohort A has been enrolling since the study initiation and will enroll up to 25 patients. At the time of amendment activation initially opening, cohort B may enroll 5 patients followed by 5 patient enrollment for cohort C. Enrollment will continue in this alternating manner with approximately 5 patient blocks at a time for these cohorts. Enrollment may be adjusted based on Medimmune/MD Anderson determined priorities and drug availability. Cohort B and C will each be 15 patients.

[figure not shown]

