Lung or liver resection will be scheduled approximately 3-weeks after the infusion of the immunotherapeutic agents. Completing up to 4 months of chemotherapy after surgical resection instead of immunotherapy (durvalumab for cohort A, durvalumab/oleclumab for cohort B, or durvalumab/monalizumab for cohort C) continuation is an option depending on the preferences of the treating physician/patient (i.e., subjects can opt out of the planned post-operatively immunotherapy). Post-operative therapy will be either chemotherapy per physician/patient choice or 4months of immunotherapy. As synchronous primary lesions are allowed in this study, the appropriate clinical care as determined by the treating multidisciplinary team for addressing the primary lesion will be allowed. Though primary resection on clinical trial prior to liver resection will not be allowed, primary resection may be simultaneous with liver resection or occur after liver resection. In addition as short course radiation therapy (5 days) is often employed for rectal primaries this will be allowed in this clinical trial as long as radiation therapy is \geq 1 week from first dose of study treatment. Factoring the occurrence of potential immune mediated AEs prior to resection, an allowance of a 3-10 weeks from neoadjuvant therapy administration will be permitted to complete metastatic and/or primary resection

As the mechanism of action of immunotherapy should not impact wound healing, patients may start adjuvant therapy as early as 4 weeks after resection, per treating physician discretion, provided they have achieved adequate status after surgery (ex. Resolution of post-operative concerns). Post-operative therapy thus can begin between 4weeks to 12 weeks post-operatively. However, if patients require >12 weeks for postoperative recovery they will not be allowed to initiate adjuvant immunotherapy.

The study design schematic is below.

Study Schematic

5.1.1 Screening visit.

If a patient is thought to be a potential candidate for the trial, then he/she can be offered participation and, if agreeable, will undergo screening procedure outlined below from D-14 to D-1. Previously conducted HIV, PT/PTT, and hepatitis testing within 30 days does not need to be repeated and will be acceptable for screening purposes (tests performed at outside laboratories as standard of care testing will be accepted).

Table 5.1-1: Screening Procedural Outline

Procedure	Screening Visit From D-14 to D-1	Notes

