13. STATISTICAL CONSIDERATIONS

13.1 Endpoints

1. Primary Endpoints

- Feasibility will be assessed by whether or not the patient successfully goes to surgery following the planned treatments, scans, and biopsy.
- Safety will be assessed by CTCAE version 4.03 for cohort A and 5.0 for cohorts B and C.

2. Secondary Endpoints

- Various immune parameters
- Response - irRECIST
- Overall survival (OS) measured from the date of study entry until death from any cause
- Relapse-free survival (RFS) from the date of study entry until relapse or death from any cause

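### Feasibility is an objective for immunotherapy before and after surgery, but the endpoint and verdict count only patients reaching surgery, so post-operative feasibility is not measured

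*Combined protocol and SAP*

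**What the plan says.** The primary objective in section 1.1 is safety and feasibility of durvalumab combinations "administered once pre-operatively and post-operatively in patients who are candidates for resection". Section 5.1 gives every cohort about four months of post-operative immunotherapy. For Cohort A, "Adjuvant therapy will consist of 4 monthly doses of durvalumab 1500mg IV"; Cohorts B and C continue both agents.

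Section 13.1 defines the feasibility endpoint: "Feasibility will be assessed by whether or not the patient successfully goes to surgery following the planned treatments, scans, and biopsy". Section 13.4 turns it into a verdict: "Each combination regimen will be considered feasible if at least 80% of patients successfully undergo surgery", and "It will be infeasible if fewer than 60% of patients can undergo surgery". Between the two limits, "consideration will be given to toxicity, clinical outcome measures, and immune changes". The sample size (13.2) and the futility rule (13.3.1) use the same surgery proportion.

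Section 5.1 describes two ways to miss the adjuvant phase after resection. Chemotherapy may be chosen instead ("subjects can opt out of the planned post-operatively immunotherapy"), and "if patients require >12 weeks for postoperative recovery they will not be allowed to initiate adjuvant immunotherapy". Section 13.3.3 sets a post-operative toxicity rule, TOXpost, among patients who begin adjuvant immunotherapy. It says that not all 25 or 15 patients are expected to enter that part, but gives no number.

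**The concern.** The objective joins two phases, and the feasibility verdict observes one. Section 13.4 attaches the word feasible to the combination regimen without saying that only the part up to surgery has been assessed. Nothing in sections 13.1 to 13.4 plans the proportion of resected patients who start adjuvant immunotherapy, or the proportion of starters who complete it.

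Section 13.4 says the results will inform the next formal trial if toxicity and feasibility are reasonable. A perioperative trial planned on that basis would need a start rate and a completion rate, and this plan does not commit to producing either. The report in section 2.6 shows the same gap: it gives 11 of 14 patients (79%) resected, but not how many of the 11 began adjuvant immunotherapy.

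**Working it through.** **1. The plan's own feasibility figure.** Inputs from 13.2: prior Beta(1.2, 0.8); 20 of 25 to surgery in Cohort A; 12 of 15 in Cohorts B and C. The posterior is Beta(1.2 + x, 0.8 + n − x), with equal-tailed 95% limits.

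- Cohort A: Beta(21.2, 5.8) gives 0.615 to 0.915, matching the stated (0.62, 0.92).
- Cohorts B and C: Beta(13.2, 3.8) gives 0.558 to 0.934, that is (0.56, 0.93) against the stated (0.57, 0.94). This difference of 0.01 at each end is a separate matter and does not affect the point.

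Both intervals are functions of n and the number resected. Adjuvant uptake is not an input.

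**2. The verdict as a function of uptake.** The limit is 0.80 × 15 = 12 resected, or 0.80 × 25 = 20. Hold the number resected at that limit and let s be the number who start adjuvant immunotherapy. The verdict is feasible for every s from 0 to 12 (or 0 to 20).

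**3. What each part of section 13 covers.**

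| Component of the objective | Planned measure |
|---|---|
| Pre-operative safety | TOX rule, 13.3.2 |
| Pre-operative feasibility | Surgery proportion, 13.1, 13.3.1, 13.4 |
| Post-operative safety | TOXpost rule, 13.3.3 |
| Post-operative feasibility | None |

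The 60-80% zone adds toxicity, clinical outcome and immune changes, but not uptake.

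**4. Precision of a start proportion.** The documents give no expected uptake, so the counts below are illustrations, not forecasts. With a flat prior and 12 resected patients, the posterior is Beta(1 + s, 13 − s).

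- s = 6: Beta(7, 7), 95% interval 0.25 to 0.75. As a share of the cohort, 6/15 = 40%.
- s = 9: Beta(10, 4), 95% interval 0.46 to 0.91. As a share of the cohort, 9/15 = 60%.

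**5. The starter count also affects how the safety rule reads.** TOXpost uses prior Beta(0.4, 1.6) and stops if the posterior probability of a rate above 0.20 exceeds 0.9. Its boundaries reproduce exactly (2/3, 3/6, 4/9, 5/13, 6/17, 7/21, 8/25). At a true rate of 0.40, exact recursion gives early-stopping probabilities of 0.89 for 25 starters and 0.73 for 15, as printed. With fewer starters, looks before the last starter give:

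| Starters | Pr(stop early) at true rate 0.40 |
|---|---|
| 15 | 0.73 |
| 12 | 0.64 |
| 9 | 0.56 |
| 6 | 0.42 |

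Counting the last look as well, the values are 0.75, 0.69, 0.62 and 0.52. A cohort that does not stop is therefore weaker reassurance when few patients start, and a reader needs the number of starters to judge it.

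**The case against.** The strongest reply is that this is a neoadjuvant trial and the verdict was always about that phase. Section 2.1.1 calls it a window study before liver resection, and section 2.6 states its hypothesis for the added cohorts in terms of neoadjuvant safety. In Cohort A tremelimumab is given only before surgery (5.1.2.1), so combination regimen can be read there as the pre-operative pair. This has force, and it means a demonstrably false verdict cannot be claimed. But section 1.1 names both phases, Cohorts B and C also receive a combination after surgery, and 13.4 does not restrict the word. If the neoadjuvant reading is intended, one sentence settles it.

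A reader might infer that half of the primary objective goes unanswered. It does not: post-operative safety has its own prior, boundaries, operating characteristics and verdict, and 13.3.3 says the rule also serves decisions about future trials. Nor is it right that nobody counts starters. TOXpost needs a running count of evaluable starters in each cohort, and starters are the proper denominator for adjuvant toxicity. What is missing is that count as a share of resected patients, and any measure of completion.

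A reader might also infer that low uptake would prove the regimen infeasible, or that heavy loss is likely. Section 5.1 makes the post-operative choice a matter of physician and patient preference, so a low start rate could reflect preference alone. The documents offer no uptake figure. Their only hint, that the operating characteristics are slightly over-estimated, does not point to a large loss.

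**Conclusion.** The point holds for post-operative feasibility only. The endpoint and verdict depend on the proportion reaching surgery, so a cohort at or above 80% resected is called feasible whatever its adjuvant uptake. That follows from the text and needs no assumption. How far the label would exceed the evidence cannot be stated, because the documents give no expected uptake. The intervals for 6 and 9 starters rest on an assumed 12 resected patients, assumed counts and a flat prior. The surgery analysis itself stands. This is a change the sponsor should make, because it alters what the trial can be said to have shown.

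**What to change.** In 13.4, state that the 80%/60% verdict concerns feasibility of the neoadjuvant phase, meaning that patients reach surgery. Then add, for each cohort, descriptive posterior estimates with 95% credible intervals for:

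1. the proportion of resected patients who start adjuvant immunotherapy within the 12-week window; and
2. the proportion of starters who complete the planned course.

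Both can come from dosing records, and neither needs a pass/fail threshold. Keep starting and completing separate, so that a patient who begins and stops early is not counted with one who never began. Report reasons for not starting (preference, late recovery, toxicity, relapse) where the record gives them.

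The cost is one paragraph and one table, with no change to treatment or visits. The study calendars in section 10 do not show that reasons for not starting are collected, so this may need one added data field and may be incomplete for patients already treated in Cohort A. The downside is a narrower feasibility claim and wide intervals.
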